4.1 Participant Disposition

The participant number, informed consent date, and protocol version at time of consent (if applicable) will be recorded in the electronic case report form (eCRF).

In addition, study completion status, the date of study completion or early withdrawal, reason for early withdrawal, adverse event number (if applicable), and description of primary reason will be recorded in the eCRF. Study completion status will be recorded as “Yes” or “No”. The reason for early withdrawal will be recorded as “Adverse Event”, “Withdrawal of consent”, “Lost to follow-up”, “Safety reasons”, “Investigator’s decision”, “Non-compliance to protocol”, or “Other”.

The duration of time in study, in days, will be calculated as (Study Completion or Discontinuation Date) - (Informed Consent date) + 1.

The following durations within the clinical trial are expected as follows, per the protocol:

- Part A: ≤49 days (63 days if on primidone)
- Part B: ≤98 days (112 days if on primidone)

4.2 Protocol Deviations

The failure to meet any eligibility criteria and the specific criteria not met will be recorded in the eCRF.

All participant data will be reviewed for the occurrence of protocol deviations. The Sponsor project team will review all protocol deviations and their major/minor classifications prior to database lock. Deviation categories will include the following:

- Procedure / Assessment outside protocol window
- Procedure / Assessment not done
- Order of Procedure / Assessment
- Missed Visit
- Visit outside protocol window
- Inclusion / Exclusion
- Informed Consent
- Study Drug Administration
- Documentation
- Study Restrictions
- COVID-19: Visit missed
- COVID-19: Assessment not performed
- COVID-19: Other
- Other

4.3 Demographic and Baseline Characteristics

The following variables are captured and/or derived for this study.

4.3.1 Age

The age in years at informed consent will be recorded in the eCRF.

4.3.2 Sex

Sex will be recorded in the eCRF as “Male” or “Female”.

4.3.3 Ethnicity

Ethnicity will be recorded in the eCRF as “Hispanic or Latino”, “Not Hispanic or Latino”, “Not reported”, or “Unknown”.

4.3.4 Race

Race will be recorded in the eCRF as one or more of the following: “Black or African American”, “American Indian or Alaska Native”, “Asian”, “Native Hawaiian or Other Pacific Islander”, “White”, “Other”, or “Not reported”. Multiple race categories can be selected.

4.3.5 Dominant Hand

Dominant hand will be recorded in the eCRF as “Right” or “Left”.

4.3.6 Height

Height in centimeters (cm) will be recorded in the eCRF.

4.3.7 Weight

Weight in kilograms (kg) will be recorded in the eCRF.

4.3.8 Body mass index

Body mass index (BMI; kg/m^2) will be derived in the eCRF, provided that weight and height are available.

4.4 Other Variables

Drug screen and alcohol results will be collected at Screening. The assessment date, time, and result will be recorded in the eCRF. The result will be recorded as "Positive" or "Negative". For positive drug screen results, those drugs of abuse testing positive will also be captured in the eCRF. Categories for positive drug tests include the following: Amphetamines, Barbiturates, Benzodiazepines, Cannabinoids, Cocaine, Methadone, Opiates, Phencyclidine, and Other.

4.5 Medical History

For those participants reporting medical history, the medical condition, onset date, ongoing indicator (Yes/No), end date (if applicable), and treatment indicator (Yes/No) will be recorded in the eCRF. Each medical history condition will be coded using Medical Dictionary for Regulatory Affairs (MedDRA) version 22.0.

4.6 Essential Tremor Medical History

Details on essential tremor medical history will be recorded in the eCRF including year of tremor onset, ET diagnosis, prior and current medications for ET (Yes/No), family history (Yes/No), ET worsening over the past 3 years (Yes/No), and effect of alcohol on ET symptoms: if symptoms decrease (Yes/No), by how much (Minimal decrease/Moderate decrease/Substantial decrease), and how many standard alcohol containing cause symptoms to decrease (<1, 1, 2, 3, >3).

4.7 Prior and Concomitant Medications

For each prior and concomitant medication, the medication name, indication, dose, frequency, route, start date, ongoing indicator, stop date (for those medications not ongoing) will be recorded in the eCRF. Each medication will be coded using the World Health Organization Drug Dictionary (WHODrug) version March 2019.

Each medication will be classified according to the study period in which its use occurred (ie, Prior, Concomitant). Prior medications are those that started and ended before the initiation of study drug. Concomitant medications are (i) those that started before initiation of study drug and continued after initiation of study drug or (ii) those that started after initiation of study drug. Any medications starting on the same day as the initiation of study drug will be considered concomitant.

For Part B, medications will be further classified as concomitant for the double-blind randomized withdrawal phase following initiation of randomized study drug. Concomitant medications from the open-label titration phase will not include events occurring within the randomized withdrawal phase. Concomitant medications taken within the safety follow-up period for a participant will be classified as occurring during his/her last phase of participation (ie, if a participant does not enter the double-blind randomized withdrawal phase any post-treatment medications will be reported as part of the open-label titration).

If the start date (or stop date) of a medication is completely unknown (ie, the day, month, and year are all missing) or only the study day is known, then the start date (or stop date) will not be imputed. Unless the stop date is before the start date of study drug, then the medication will be considered concomitant.

For a partial start date of medication, the following conventions will be used for imputing the start date:

- If the year is present and the month and day are missing, then the month and day will be set to January 1.
- If the year and day are present and the month is missing, then the month will be set to January.
- If the year and month are present and the day is missing, then the day will be set to the first day of the month.
- If the imputed start date of medication is after the non-imputed end date of medication, then the start date will be set to the stop date of medication.

For a partial stop date of medication, the following conventions will be used for imputing the stop date:

- If the year is present and the month and day are missing, then the month and day will be set to December 31.

- If the year and day are present and the month is missing, then the month will be set to December.
- If the year and month are present and the day is missing, then the day will be set to the last day of the month.

4.8 Study Drug Exposure

For study drug exposure, date of administration, time of administration, and dose recorded in the eCRF. The overall duration of exposure to study drug (in days) will be calculated for Study Part, by dose level and overall, as follows:

- Duration of Exposure to study drug (days) = Date of Last Dose – Date of First Dose + 1

Overall percent compliance will be calculated as the total number of days drug was received divided by the total number days drug was expected to be received during the subject's participation in the study. In addition, overall compliance will also be categorized as:

- Compliance < 80%
- $80\% \leq \text{Compliance} \leq 120\%$
- Compliance >120%

In Part B, separate compliance estimates will be calculated for the open-label titration phase and the double-blind, randomized withdrawal phase.

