If at any point during the open-label titration phase a participant does not tolerate escalation and the Investigator returns the participant to a lower dose level, the participant will continue according to the schedule outlined above, but no further dose changes will be allowed. The Investigator should discuss the decision to continue at a lower dose level with the Sponsor and Medical Monitor. Participants can only change to a lower dose level once, and no dose changes may occur after Day 36.

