6.6. Dose Modification

No dose modifications are permitted in Part A or the Part B double-blind randomized withdrawal phase.

In the Part B open-label titration phase, participants may return to a lower dose of PRAX-944 after escalating due to tolerability or safety concerns. The Investigator should discuss the decision to continue at a lower dose level with the Sponsor and Medical Monitor. Participants can only change to a lower dose level once. No dose changes are permitted after Day 36.

The Sponsor may discontinue any dose of PRAX-944 based on ongoing monitoring of safety and tolerability.

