7.1.1. Temporary Discontinuation

Temporary discontinuations of study drug is allowed on a case-by-case basis, pending approval from the Sponsor.

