For Part B, AEs will be identified as TEAEs for the double-blind randomized withdrawal phase based on the first dose of randomized study drug. AEs reported during the open-label titration period will not include events occurring within the randomized withdrawal phase. Events occurring within the safety follow-up period for a participant will be classified as occurring during his/her last phase of participation (ie, if a participant does not enter the double-blind randomized withdrawal phase any post-treatment AEs will be reported as part of the open-label titration).

If an AE is imputed for Part B and is attributed to the open-label titration or double-blind randomized withdrawal phase, it should be checked for plausibility. If an imputed AE onset date could potentially have started during a subsequent phase (eg, if the onset date had been imputed as the 1st of a particular month falling into the open-label titration phase, but it plausibly could have started later in the month during the double-blind randomized withdrawal phase), the AE should be identified as TEAE for any plausible phases.

For each AE, a treatment emergent flag will be calculated using the recorded AE start date (or imputed start date, where applicable). Additional treatment emergent flags will be created for each dose level.

Adverse events occurring during PRAX-944 titration will be assigned to a dose level based on the onset date/time of the adverse event relative to the first dose date/time of study drug administration at each dose level. Specifically, if an AE occurs after the first dose of study drug at a participant's actual dose level and prior to the first dose at the next dose level, the AE will be assigned within a participant's actual dose level in the adverse event summary. If the date was imputed and could plausibly occurred during a subsequent dose level, the AE should be identified as TEAE for subsequent and plausible dose levels.

If the time is missing (either for the adverse event or study drug administration), then the AE date (and relative study day) will be used to determine in which dose level the AE should be assigned, assuming that the AE occurred after the dose taken on the specified day. An adverse event will only be reported within the dose level in which the AE started (eg, an adverse event that starts within the 40 mg dose level and continues into the 80 mg dose level will only be reported in the 40 mg dose level).

[figure not shown]

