5 ANALYSIS METHODS

Analysis will be carried out using SAS® (version 9.4 or newer, SAS Institute Inc, Cary, NC). Templates for the summary tables, figures, and participant data listings will be available separately. Data listings will include all data recorded for all enrolled participants; where captured, data entered for screen failure participants will be flagged in the listings.

For all data displays, separate summaries will be generated for each part and phase (open-label titration and double-blind randomized withdrawal) of the clinical trial.

- Part A: All summaries except those for adverse events will use a single "PRAX-944 Overall" column. Summaries of adverse events will use the following columns: "PRAX-944 20 mg qAM", "PRAX-944 40 mg qAM ", and "PRAX-944 Overall".
- Part B: Summaries of disposition and PK will be presented for all of Part B (i.e., not by phase) and will use a single "PRAX-944" column.
- Part B Open-label Titration: Summaries of demographics, baseline characteristics, medical history, prior and concomitant medications, study drug exposure, efficacy, and all safety except adverse events will include a "PRAX-944 Overall" column. Summaries of adverse events will include columns for "PRAX-944 20 mg qAM", "PRAX-944 40 mg qAM ", "PRAX-944 60 mg qAM ", "PRAX-944 80 mg qAM ", "PRAX-944 100 mg qAM ", "PRAX-944 120 mg qAM ", and "PRAX-944 Overall".
- Part B Randomized Withdrawal: Summaries of demographics, baseline characteristics, medical history, prior and concomitant medications, study drug exposure, efficacy, and all safety except adverse events will include the columns "Placebo" and "PRAX-944" for the randomized withdrawal phase. Summaries of adverse events will include columns for "Placebo" and "PRAX-944".

Descriptive statistics for continuous data will include number of participants (n), mean, standard deviation (SD), median, minimum, and maximum. Summaries of change from baseline variables will include only participants who have both a baseline value and corresponding value at the timepoint of interest. Descriptive statistics for categorical data will include frequency and percentage. Where appropriate, descriptive statistics may be presented with 95% confidence intervals (CIs).

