5.8 Safety Analyses

For all safety variables, descriptive statistics will be presented by study part, treatment group, and visit (where applicable) using the safety analysis set and randomized withdrawal safety analysis set. In summaries of change from baseline safety variables, only participants with both baseline and change from baseline values will be included. No formal hypothesis testing will be performed for any safety variable.

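### By-dose exposure duration in SAP 4.8 counts higher-dose days as days at the lower dose after a permitted Part B step-down (minor)

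*SAP*

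**What the plan says.** SAP 4.8 states that duration of exposure "will be calculated for Study Part, by dose level and overall". The only formula begins "Duration of Exposure to study drug (days) = Date of Last Dose" and continues with the subtraction of the first dose date and the addition of 1. The same section records the date, time and dose of administration in the eCRF. It bases compliance separately on the number of days drug was received.

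Protocol 6.6 says that in the Part B open-label phase "participants may return to a lower dose of PRAX-944 after escalating due to tolerability or safety concerns". This may happen once. Protocol 4.1.2.2.1 adds that "no dose changes may occur after Day 36" and that the lower dose is then held. SAP 2.2 describes the same step-down, so the SAP foresees it.

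SAP 4.10.1 has its own rule for placing adverse events at a dose level. An event belongs to the participant's actual level if it starts after the first dose at that level "and prior to the first dose at the next dose level". SAP 4.8 has no equivalent rule for a level taken in two separate blocks.

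**The concern.** The titration schedule passes through every level from 20 mg upward. A return to a lower scheduled level is therefore a return to a dose already taken, and that dose then occupies two blocks with higher-dose days between them. A span from first to last date at that dose takes in the days between, although the participant was on a higher dose.

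Safety and tolerability is the Part B primary objective. SAP 5 says of the open-label phase "Summaries of adverse events will include columns for" each dose from 20 to 120 mg. Time spent at each dose is natural context for those columns. As written, the exposure rule and the adverse event rule place the same days differently. An event starting while the participant was on 120 mg is assigned to 120 mg only, but those days are counted as exposure to both 120 mg and the lower dose. The participants affected are those who did not tolerate escalation.

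**Working it through.** **Inputs.** Planned schedule (Protocol 6.1.2.1 and Table 4): 20 mg Days 1–3, 40 mg Days 4–7, 60 mg Days 8–14, 80 mg Days 15–21, 100 mg Days 22–28, 120 mg Days 29–42. One step-down, no later than Day 36, then held (Protocol 4.1.2.2.1 and 6.6). Daily dosing with no missed doses is assumed.

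**The plan's own figures first.** With no step-down, last − first + 1 gives 3, 4, 7, 7, 7 and 14 days, total 42. This matches the schedule, so the formula is correct for anyone who follows it.

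**After a step-down.** Formula = last day at the lower dose − first day at it + 1. Days taken = first block + second block.

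| Return | Return day | Formula | Days taken | Overcount | Sum of all levels by formula |
|---|---|---|---|---|---|
| 120 to 100 mg | 30 | 42−22+1 = 21 | 7+13 = 20 | 1 | 43 |
| 120 to 100 mg | 32 | 42−22+1 = 21 | 7+11 = 18 | 3 | 45 |
| 120 to 100 mg | 36 | 42−22+1 = 21 | 7+7 = 14 | 7 | 49 |
| 120 to 80 mg | 36 | 42−15+1 = 28 | 7+7 = 14 | 14 | 56 |
| 120 to 20 mg | 36 | 42−1+1 = 42 | 3+7 = 10 | 32 | 74 |

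The true sum is 42 in every row. The overcount equals the days spent above the lower dose between the two blocks. For a one-level return that is 1 to 7 days (1 to 4 for 40 to 20 mg, because the 40 mg step lasts 4 days). For 120 to 100 mg the formula gives 21 whatever the return day from 30 to 36, so it cannot tell an early step-down from a late one.

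If by-dose duration runs over all of Part B and the participant stays on 100 mg to Day 56, the Day 36 case gives 56−22+1 = 35 against 7+7+14 = 28. The overcount is again 7.

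**Effect on a summary of days at 100 mg.** The documents give no step-down rate, so the number returning is an assumption. Let m of 12 participants return from 120 to 100 mg and the rest take 7 days at 100 mg.

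- m = 1: formula mean (11×7+21)/12 = 8.17. Days taken give (11×7+20)/12 = 8.08 for a Day 30 return and (11×7+14)/12 = 7.58 for Day 36. The SD by formula is 4.04, against 3.75 (Day 30) or 2.02 (Day 36).
- m = 4: formula mean (8×7+4×21)/12 = 11.67. Days taken give (8×7+4×20)/12 = 11.33 (Day 30) or (8×7+4×14)/12 = 9.33 (Day 36).

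The median is 7 in all of these cases. The maximum is 21 by formula against 20 or 14 taken.

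**The case against.** The strongest reply is that the affected output is not shown to exist. For Part B open-label exposure, SAP 5 names only an overall PRAX-944 column, and it gives dose-level columns only for adverse events. Table templates are held separately, and they or the programmer may sum separate blocks. This stands as a limit on what can be said about a reported table. It does not remove the point, because SAP 4.8 requires the by-dose calculation and nothing in the text says to sum blocks.

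A reader might take the Day 36 figures as typical. The documents do not support that. Day 36 is the last permitted day and gives the largest one-level overcount. A participant who does not tolerate an escalation may well return sooner, and then the difference can be as small as one day. The 120 to 20 mg case is not forbidden, but it sits badly with the stated aim of dosing at the highest tolerated level.

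A reader might also object that the span counts off-drug days, since Protocol 7.1.1 says "Temporary discontinuations of study drug is allowed on a case-by-case basis". That is not an error. Last minus first plus 1 is a calendar duration, and including a gap in it is a convention. The days on which drug was received already enter the compliance figure in the same section.

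Finally, a reader might infer that adverse event rates by dose are distorted. The planned summaries are counts and percentages of participants, none uses exposure days as a denominator, and the dose assignment has its own rule. SAP 5.8 adds "No formal hypothesis testing will be performed for any safety variable".

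**Conclusion.** The rule is wrong as written for a Part B participant who steps down to a level already taken. It overstates days at the lower dose by 1 to 7 for a one-level return, and by more for a larger drop. The size for any one participant follows exactly from the schedule and the return day, assuming daily dosing. The size in a summary cannot be known, because neither the number of step-downs nor their timing is given.

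The severity is minor. The effect is confined to a descriptive by-dose duration whose display is not visible. Overall duration, compliance, adverse event incidence and dose assignment, and efficacy are unaffected. SAP 5 calls for listings of all recorded data, so the true dates and doses can be recovered.

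**What to change.** In SAP 4.8, for duration by dose level, apply last dose date minus first dose date plus 1 to each continuous block at that dose and sum the blocks. Define a block as a run of administrations at one dose with no other dose in between. Keep the existing formula for overall duration.

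Check on the Day 36 case: 100 mg = (28−22+1) + (42−36+1) = 14 and 120 mg = 35−29+1 = 7, so the levels sum to 3+4+7+7+14+7 = 42, equal to overall duration. The higher-dose days then count only where the adverse event rule places events.

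Counting dosing days by level while leaving overall duration as a calendar span is less suitable. The two would disagree after any interruption, for example 39 against 42 with three days off inside the 60 mg block. Summing calendar blocks keeps a gap inside a block in both figures.

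The cost is one changed derivation line. The dates and doses are already collected, and only figures for participants who stepped down would change.

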k On Day 1 and 42, study drug must be administered in the clinic on an empty stomach (at least 1 hour before breakfast, which will be provided at the site) and the participant should be observed in the clinic for approximately 6 hours before discharge. On all other days, participants should be instructed to take study drug at least 1 hour before breakfast in the morning at home. The escalation schedule is as follows: 20 mg, Day 1 through Day 3; 40 mg, Day 4 through Day 7; 60 mg, Day 8 through Day 14; 80 mg, Day 15 through Day 21; 100 mg, Day 22 through Day 28; and 120 mg, Day 29 through Day 42. Participants will receive blinded study drug on Days 43 to 56. During blinded treatment period, participants should take the same number of tablets per day as taken during Days 36 to 42.

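### SAP 4.8: the first-to-last-dose span, applied by dose level, overstates exposure at the level a Part B participant steps back to

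*SAP*

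**What the plan says.** SAP 4.8 gives a single exposure formula, "Duration of Exposure to study drug (days) = Date of Last Dose – Date of First Dose + 1", which "will be calculated for Study Part, by dose level and overall". The underlying data are dose records: "date of administration, time of administration, and dose recorded in the eCRF". Compliance, in the same section, is built differently, from a count of days on which drug was received.

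The planned Part B open-label schedule (SAP Appendix 1, Part B schedule, footnote k; the same durations are in Protocol 6.1.2.1) is "20 mg, Day 1 through Day 3; 40 mg, Day 4 through Day 7; 60 mg, Day 8 through Day 14", then "80 mg, Day 15 through Day 21; 100 mg, Day 22 through Day 28; and 120 mg, Day 29 through Day 42".

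Protocol 6.6 allows a step back in that phase: "participants may return to a lower dose of PRAX-944 after escalating due to tolerability or safety concerns". Protocol 4.1.2.2.1 limits it: "Participants can only change to a lower dose level once, and no dose changes may occur after Day 36". SAP 2.2 repeats that a participant returned to a lower level has no further dose changes. Elsewhere it cannot happen: "No dose modifications are permitted in Part A or the Part B double-blind randomized withdrawal phase".

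The SAP has no rule for a dose level taken in two separate blocks.

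**The concern.** A first-to-last span equals the time on a dose only if that dose is taken in one unbroken block. A step-down breaks this condition. The participant takes the lower dose, moves up, then returns to the lower dose until the end of the phase. The span for the lower dose runs across the whole period, including the days at the higher dose, and those days are also counted at the higher level.

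The error has one direction: it inflates the lower level. It arises only in participants who came down for tolerability or safety reasons. Dose-level time on drug is the natural background for the adverse event tables, which SAP Section 5 lays out in six dose columns for the Part B titration. With about 12 participants planned, and at most 24 before replacements, a few step-downs could visibly shift a dose-level exposure summary.

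**Working it through.** **Inputs.** The formula and its use by dose level come from SAP 4.8. The schedule comes from SAP Appendix 1. The limits of one step-down and no change after Day 36 come from Protocol 4.1.2.2.1. First and last dose are read as first and last dose at the level concerned, which is the reading that gives a dose-level duration a meaning. The participant is assumed to be on schedule until the step-down and to miss no doses.

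**Reproducing the planned figures.** Without a step-down the formula gives:
- 20 mg: 3 − 1 + 1 = 3
- 40 mg: 7 − 4 + 1 = 4
- 60 mg: 14 − 8 + 1 = 7
- 80 mg: 21 − 15 + 1 = 7
- 100 mg: 28 − 22 + 1 = 7
- 120 mg: 42 − 29 + 1 = 14

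The total is 42 days, which matches the schedule. Part A gives 7 and 7 days, also correct.

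**With a step-down.** Let the lower dose first be taken on Days a to b, and let s be the first day back on it, continuing to Day 42.
- Formula: 42 − a + 1
- Days actually taken: (b − a + 1) + (42 − s + 1)
- Excess: s − b − 1, which is the number of days spent at the higher dose or doses

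| Step-down | First day back (s) | Formula, level returned to | Days taken | Excess | Sum of levels by formula (42 days dosed) |
|---|---|---|---|---|---|
| 40 to 20 mg | 5 | 42 − 1 + 1 = 42 | 3 + 38 = 41 | 1 | 43 |
| 80 to 60 mg | 17 | 42 − 8 + 1 = 35 | 7 + 26 = 33 | 2 | 44 |
| 120 to 100 mg | 36 | 42 − 22 + 1 = 21 | 7 + 7 = 14 | 7 | 49 |
| 120 to 60 mg | 36 | 42 − 8 + 1 = 35 | 7 + 7 = 14 | 21 | 63 |
| 120 to 20 mg | 36 | 42 − 1 + 1 = 42 | 3 + 7 = 10 | 32 | 74 |

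**Range.** All permitted combinations were enumerated: first day back from Day 5 to Day 36, to any level below the current one. There are 4×1 + 7×2 + 7×3 + 7×4 + 7×5 = 102 cases. Every case overstates the level returned to. The excess is 1 to 7 days in the 32 one-level cases and 1 to 32 days over all cases. In each case the other levels are exact and the overall span is 42 days, as it should be.

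**Continuation to Day 56.** If the participant is randomized to stay on drug and those 14 days are added at the same level, the excess does not change. For 120 to 100 mg on Day 36 the formula gives 56 − 22 + 1 = 35, against 14 + 14 = 28 days taken.

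**The case against.** The strongest reply is that little depends on this variable. SAP Section 5 names a single overall PRAX-944 column for open-label exposure; only adverse events get dose columns. Adverse events are assigned to dose by onset relative to dosing dates (SAP 4.10.1), not by the 4.8 duration, and the planned summaries are participant incidences with no exposure-adjusted rate in the visible text. The table templates are held separately, so whether dose-level exposure is displayed cannot be seen. All of this stands, and it keeps the point minor. SAP 4.8 nevertheless calls for the dose-level derivation, and as written it returns a wrong number after a step-down.

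It can also be said that SAP 4.8 does not forbid summing by block. That is true, but the one formula stated is a span and no other instruction is given.

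The Day 36 examples are upper-end cases: 7 days is the largest one-level excess, and drops of several levels are permitted by the wording but not described as usual. The return after two days at 80 mg, with an excess of 2, shows how small the effect can be.

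Three stronger readings are tempting, and the documents do not support them.
- A reader might infer that a participant switched to placebo is credited with 56 days on PRAX-944. SAP Section 5 already summarizes exposure by phase, with placebo and PRAX-944 columns for the withdrawal phase, and SAP 3.3 gives that phase its own safety set.
- A reader might infer that the error touches Part B's primary objective as an evaluation by dose. The objective (Protocol 3.2, SAP 2.1) is safety and tolerability in participants with ET and does not mention dose.
- A reader might treat days off drug during a temporary discontinuation (Protocol 7.1.1) as the same fault. A first-to-last span is a measure of duration, and SAP 4.8 captures missed days through compliance.

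**Conclusion.** The point holds, as a minor one. Followed as written, SAP 4.8 overstates exposure at the one dose level a Part B participant returns to, by exactly the days spent above it: 1 to 7 days for a one-level step-down and up to 32 days in the extreme permitted case. The dose levels then sum to 43 to 74 days when 42 were dosed.

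This rests on reading first and last dose within each level, and on titration to schedule before the step-down. It does not mean that dose-level exposure is wrong in general. The higher levels, overall duration, Part A and compliance are unaffected by step-down, as are adverse event dose assignment and all efficacy results. The documents do not say how many step-downs occurred or were expected, so the effect on any summary table cannot be computed.

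**What to change.** In SAP 4.8, define exposure at a dose level as the number of days on which that dose was taken, summed over separate blocks, from the administration dates and doses already in the eCRF. Keep the first-to-last span for overall duration. In every step-down case above the levels then add up to 42 days.

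The cost is one sentence in the SAP and a small programming change. No new data are needed, and no dosing rule or other analysis changes.
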